Smartphone-based CBT for OCD can address gaps in access to treatment, offering standardized, high-quality, empirically-based interventions in a low-cost and accessible format. Additionally, given the low rate of doctoral-level clinicians specializing in CBT for OCD treatment, it would be advantageous to establish whether mobile app-based CBT can be administered effectively with assistance from trained bachelors-level coaches who are supervised weekly by licensed, doctoral-level psychologists. This would greatly enhance scalability of the treatment.

II. SPECIFIC AIMS

The overarching purpose of this project is to test the feasibility, acceptability, and efficacy of mobile-app-delivered CBT for OCD. We accomplish this through Specific and Exploratory Aims 1-3.

Specific Aim 1: In a well-powered, randomized-controlled trial, we will test the efficacy of the active treatment arm (Perspectives OCD) compared to a supportive attentional control (HealthWatch) in reducing primary (i.e., OCD symptom severity, measured via Y-BOCS) and secondary outcomes (e.g., quality of life, depression, social and occupational functioning) at week 12.

Primary Hypothesis: We hypothesize that participants receiving app-based CBT for OCD will have greater improvement in Y-BOCS scores than those in the supportive attentional control condition at treatment endpoint (week 12).

Secondary Hypothesis: We hypothesize that participants receiving app-based CBT for OCD will have greater improvement on secondary clinical outcome measures (i.e., depression (QIDS-SR), functional impairment (WSAS), and quality of life (Q-LES-Q)) than those in the supportive attentional control condition at treatment endpoint (week 12).

Exploratory Aim 2: Feasibility and Acceptability

Hypothesis: We hypothesize that app-delivered CBT for OCD will be feasible (based on drop-out rates) and acceptable (based on descriptive statistics of patient satisfaction, app use, and app feedback as well as qualitative feedback) to individuals with OCD.

Exploratory Aim 3: Maintenance of gains (Y-BOCS, QIDS-SR, Q-LES-Q-SF, WSAS) at follow-up (week 24).

Hypothesis: There will be no significant difference between the primary and secondary outcomes measured at treatment endpoint (week 12) and end of follow-up (week 24) in the group that participated in the app-CBT condition.

III. SUBJECT SELECTION

Overview:

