Primary endpoint: Difference in OCD severity (Y-BOCS) at the end of treatment (i.e., week 12 assessment).

Hypothesis 1: Participants receiving app-CBT will have lower Y-BOCS scores than those in the supportive attentional control condition at treatment endpoint (week 12).

Secondary endpoints: Difference in secondary clinical outcomes at the end of treatment (i.e., week 12 assessment)

Hypothesis 2: Participants who receive the app-CBT will have better scores on secondary clinical outcome measures than those in the supportive attentional control condition at treatment endpoint (week 12) with respect to:

H2.1: depression severity, as measured by the QIDS-SR, where lower scores are better.

H2.2: functional impairment, as measured by the WSAS, where lower scores are better.

H2.3: quality of life, as measured by the Q-LES-Q-SF, where higher scores are better.

Exploratory endpoint 1: Feasibility and Acceptability

Hypothesis 3.1: Drop-out from app-delivered CBT for OCD will not be higher than drop-out from the supportive attentional control condition, which will indicate feasibility.

Hypothesis 3.2: Patient satisfaction ratings (i.e., CSQ total scores) in the group receiving app-delivered CBT for OCD will not be lower than those in the supportive attentional control condition, which will indicate acceptability.

Hypothesis 3.3: App-delivered CBT for OCD will be acceptable to individuals with OCD based on descriptive statistics of app use, app feedback, and qualitative feedback comments.

Exploratory endpoint 2: Maintenance of gains (Y-BOCS, QIDS-SR, WSAS, Q-LES-Q-SF) during follow-up (at 3-month and 12-month follow-up assessments).

Hypothesis 4: At the 12-month follow-up assessment, participants who received app-CBT will have lower Y-BOCS scores than those in the supportive attentional control condition.

Exploratory endpoint 3: Treatment utilization for OCD concerns following the 3-month follow-up.

Hypothesis 5: Participants assigned to the app-CBT treatment condition will be less likely to seek additional treatment for OCD than participants assigned to the supportive attentional control condition prior to the 12-month follow-up assessment.

C. Statistical methods

For all statistical analyses, we will use a Type I error probability of 0.05 to determine significance unless otherwise noted.

Primary endpoint: Difference in OCD severity (Y-BOCS) at the end of treatment (i.e., preliminary efficacy for primary OCD symptoms)

Analysis:

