We will use the same hierarchical mixed modeling approach as described for the primary endpoint to examine significant differences in secondary outcome measures (i.e., depression severity (H2.1), functional impairment (H2.2), and quality of life (H2.3)) at post-treatment between participant in the app-CBT vs. supportive attentional control conditions. We will not adjust for multiple testing among secondary outcomes based on the recommendation of Cook and Farewell (1996), who argue that multiplicity adjustments are not necessary if separate test results are interpreted marginally and address different aspects of the patient experience and decision-making process rather than alternative assessments of efficacy.

Exploratory endpoint 1: Assess feasibility and acceptability

Analysis:

We will test feasibility and acceptability by examining:

- H3.1: Refusal and dropout rates and reasons, by group: Drop-out rates by treatment (app-CBT vs. supportive attentional control) will be compared using logistic regression. Drop-outs will be defined operationally as participants who do not complete either an endpoint or follow-up assessment of the primary outcome measures (Y-BOCS), as well as participants in the CBT arm who do not use the app or participants in the HealthWatch arm who do not use the website at least once between assessments (i.e., at least once between baseline and week 6 and at least once between week 6 and week 12). We will use one-tailed tests to examine if the odds of drop-out in the app-CBT group are higher; if non-significant, we will interpret the results as an indication that the app-CBT treatment is feasible in comparison to the supportive attentional control condition; conversely, significantly higher odds of drop-out in the app-CBT condition would indicate a lack of feasibility.

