- H3.2: We will analyze patient satisfaction, as measured by on Client Satisfaction Questionnaire (CSQ) in a hierarchical mixed model (i.e., GLMM) that will include time (categorical; week 6 and week 12), treatment (app-CBT vs. supportive attentional control), and their interaction as fixed effects, and will model time as a repeated measure using a compound symmetry covariance structure. We will test group differences with one-tailed tests in patient satisfaction (testing for lower satisfaction) at both week 6 and week 12 using specific contrasts with $\alpha=.025$ to adjust for multiple testing. Non-significant results of these tests will be interpreted as indications of treatment acceptability, while lower satisfaction will be interpreted as indicating a lack of acceptability.
- H3.3: Quantitative (i.e., app feedback questionnaires, uMARS) and qualitative participant feedback about app features will be summarized for the app-CBT group using descriptive statistics.

Exploratory endpoint 2: Maintenance of gains (Y-BOCS, QIDS-SR, WSAS, Q-LES-Q-SF) at follow-up (week 24).

Analysis:

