Andersson et al., 2012) to $d=0.55$ in a trial of iCBT vs. internet-based progressive relaxation therapy (n=179; Kyrios et al., 2018) and $d=0.52$ in a trial of CBT vs. stress management training (n=73; Whittal, Woody, McLean, Rachman, & Robichaud, 2010). In the process of evaluating effect sizes from previous trials, we did not differentiate between internet-delivered CBT and face-to-face CBT, because a meta-analysis including 13 RCTs that directly compared these two treatment modalities in patients with various psychiatric and somatic conditions (total N=1053) showed a pooled effect size (Hedges' g) at post-treatment of -0.01 (95% CI: -0.13 to 0.12; G. Andersson, Cuijpers, Carlbring, Riper, & Hedman, 2014); of note, though, this direct comparison has not been done in trials with patients with OCD. Furthermore, in the wake of the COVID-19 pandemic, various negative mental health states and stressors – including anxiety, worry, depression, loneliness, financial strain, and trauma symptoms – have increased in the US population (e.g., Fowers & Wan, 2020). The variability of these negative mental health states and stressors will likely be higher than during non-pandemic times as multiple waves of the pandemic and state-wide measures of social interaction restrictions sweep the nation in the foreseeable future. In response, we used a standard deviation of 1.1 (instead of the standardized 1.0) in our power calculations to allow for a 10% increase in the variability of symptom severity estimates during the ongoing effects of the COVID-19 pandemic and its socioeconomic aftermath. Lastly, we assumed a conservative drop-out rate of 20% by end of treatment, based on the dropout numbers reported in a meta-analysis of 18 studies targeting self-help treatments for OCD, where studies with self-administered treatment without therapist contact had a drop-out rate of approximately 40%, compared to drop-out rates of 17-20% in treatments with minimal to low therapist contact (Pearcy, Anderson, Egan, & Rees, 2016); the meta-analysis by Ost et al. (2015) reported an estimated dropout rate of 15.5% from in-person CBT treatment.

VII. RISKS AND DISCOMFORTS

A. Complications of surgical and non-surgical procedures

Not applicable

B. Drug side effects and toxicities

Not applicable

C. Device complications/malfunctions

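### Exploratory H3.1 and H3.2 read a non-significant one-tailed test for 'worse' as feasibility or acceptability, with no margin and no inconclusive outcome, so imprecise data favour the positive reading

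*Combined protocol and SAP*

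**What the plan says.** Section VI.B (Study endpoints, Exploratory endpoint 1) words both hypotheses as 'not worse' claims. Under H3.1, drop-out from the app "will not be higher than drop-out from the supportive attentional control condition, which will indicate feasibility". Under H3.2, CSQ scores in the app group "will not be lower than those in the supportive attentional control condition, which will indicate acceptability".

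Section VI.C (Statistical methods, Exploratory endpoint 1) gives the decision rules.

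- **H3.1:** drop-out is compared by logistic regression, one-tailed for higher odds on the app. Then: "if non-significant, we will interpret the results as an indication that the app-CBT treatment is feasible in comparison to the supportive attentional control condition". Only a significant excess counts as a lack of feasibility. Drop-out here covers missing Y-BOCS assessments and also, for each interval between visits up to week 12, "participants in the CBT arm who do not use the app or participants in the HealthWatch arm who do not use the website".
- **H3.2:** CSQ is compared in a mixed model, with one-tailed contrasts for lower satisfaction at weeks 6 and 12. Each uses alpha .025 "to adjust for multiple testing. Non-significant results of these tests will be interpreted as indications of treatment acceptability".

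Neither rule has a margin, a confidence-interval criterion, a power statement or a third outcome. Section VI.D sizes the trial for the primary Y-BOCS contrast only. Section II labels the aim exploratory, but opens: "The overarching purpose of this project is to test the feasibility, acceptability, and efficacy of mobile-app-delivered CBT for OCD".

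**The concern.** A claim that drop-out is not higher, or satisfaction not lower, needs data that rule out a difference large enough to matter. The stated rules ask only whether the data prove the app worse, and treat failure to prove it as support for the opposite claim. A result too imprecise to decide is therefore booked as favourable, and a smaller or noisier trial has a better chance of a favourable reading than a larger one with the same truth.

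At stake is a published statement that the app is feasible or acceptable relative to control which the data may not support. Feasibility and acceptability are two of the three things the project says it sets out to test.

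**Working it through.** **Inputs.** 120 randomized (Section III overview), allocated 1:1 (Study Procedures), so 60 per arm. Type I error 0.05 (Section VI.C), applied one-sided for H3.1 and .025 per contrast for H3.2. Control drop-out is assumed to be 20%, because Section VI.D says "we assumed a conservative drop-out rate of 20% by end of treatment". That is an overall planning rate, and the H3.1 definition is broader, so control rates of 10-40% are also shown. No covariates are named for the logistic model, so each arm is treated as binomial.

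**1. The plan's own figure.** No sample size is given for H3.1 or H3.2. The only one is 116 for the primary contrast. With effect 0.76, SD 1.1, two-sided 0.05 and power 0.90, a t-based calculation gives 46 per arm; 46/0.80 = 57.5, rounded up to 58, or 116 in total. It reproduces and is not in dispute.

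**2. How often H3.1 reads 'feasible'.** By normal approximation, with p1 the app rate, p0 the control rate and p the mean of the two:

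power = Phi{ [(p1 - p0) - 1.645 x sqrt(2p(1-p)/n)] / sqrt(p1(1-p1)/n + p0(1-p0)/n) }

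For 30% versus 20%, n = 60: [0.10 - 1.645 x 0.0791] / 0.0785 = -0.38, so power is 0.35 and 'feasible' is returned 65% of the time.

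Exact binomial enumeration (score and likelihood-ratio tests, then Wald), control 20%:

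| True app drop-out | P(read as feasible) |
|---|---|
| 20% | 95% |
| 25% | 84% |
| 30% | 64-65% |
| 35% | 41-43% |
| 40% | 22% |

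Over control rates of 10-40%, the figure is 54-71% for a true 10-point excess and 29-51% for 15 points.

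**3. Dependence on precision alone.** For a true 30% versus 20% (Wald), 'feasible' is returned 84% of the time at 20 per arm, 65% at 60, 45% at 120 and 19% at 240. Only 60 is this trial's size; the others show the direction.

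**4. A worked result.** Suppose 19/60 versus 12/60 drop out (32% versus 20%).

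- Odds ratio = (19 x 48)/(41 x 12) = 1.85; log = 0.617.
- SE = sqrt(1/19 + 1/41 + 1/12 + 1/48) = 0.426; z = 1.45; one-sided p = .07. Score and likelihood-ratio tests also give .07. The rule reads this as feasible.
- Difference = 0.1167. One-sided 95% upper limit = 0.1167 + 1.645 x sqrt(0.3167 x 0.6833/60 + 0.2 x 0.8/60) = 0.1167 + 0.1303 = 0.247, an excess of about 25 points.

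The same percentages at 100 per arm (32 versus 20) give p = .03 and the opposite verdict.

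**5. H3.2.** The plan gives no CSQ SD, so a true deficit of 0.3 SD is assumed. A two-sample noncentral-t calculation, which ignores any precision gained from the repeated measures, makes one contrast non-significant 63% of the time at 60 per arm and 69% at 48 (60 x 0.80) with alpha .025. At .05 the figures are 50% and 57%. The plan does not say how the two weeks combine, so no joint figure is given.

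**The case against.** The aim is exploratory, no primary or secondary conclusion depends on it, and no progression decision in the documents hangs on it. The wording is hedged (an indication) and comparative. Section VI tabulates drop-out by reason and arm, compares dropouts with completers, and adds app feedback, uMARS and qualitative comments under H3.3. A reader of a 32% versus 20% result would see both rates. All of this stands and limits the harm. It does not alter the stated rule, because none of that material enters it.

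A reader might infer a stronger point from Section VI.D, which reports that "studies with self-administered treatment without therapist contact had a drop-out rate of approximately 40%, compared to drop-out rates of 17-20" percent with minimal to low contact, and treat 40% versus 20% as the plan's own feasibility benchmark. The documents do not support that. The figures justify an overall 20% attrition assumption and set no feasibility threshold. They contrast no contact with some contact, whereas both arms here have an assigned coach. At that 20-point gap the test also has about 78% power, so it is the least telling case; the weakness shows at 10-15 points.

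A reader might also take the .025 split in H3.2 as a separate error. If either week alone can trigger a finding of lower satisfaction, the split is ordinary control of that error. It only aggravates the main problem, because here non-significance is the favourable result.

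**Conclusion.** The point holds for the interpretive rules of H3.1 and H3.2. The plan states 'not worse' claims, tests only for worse, and assigns every undecided result to the favourable side. The percentages depend on 60 per arm, a one-sided 0.05 test and the assumed control rate, but the direction does not: the problem is present across control rates of 10-40%. The excesses and the CSQ deficit are illustrations, since the documents state no unacceptable difference. Nothing here bears on the Y-BOCS or secondary efficacy analyses, or shows that the app will prove less feasible than control. This should be fixed before analysis.

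**What to change.** - Delete the two statements in Section VI.C that read non-significance as feasibility or acceptability, and reword H3.1 and H3.2 in Section VI.B to match.
- Report the drop-out difference (app minus control, on the plan's definition) and the CSQ differences at weeks 6 and 12, each with a confidence interval. For CSQ this suits Section II, where Aim 2 rests acceptability on descriptive statistics.
- Make a 'not worse' claim only if the sponsor fixes a margin before analysis and the one-sided 95% limit excludes it. For CSQ require this at both weeks, which needs no alpha split. Otherwise call the result inconclusive.

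The cost is SAP wording, with no new data or patients. The downside is fewer positive verdicts. At equal 20% drop-out and 60 per arm, 'feasible' falls from 95% to 40%, 67% or 86% for illustrative margins of 10, 15 or 20 points. In return, a false 'feasible' when the true excess equals a 15-point margin falls from 41-43% to about 5%.

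For 80% power at equal 20% drop-out, n per arm = 2 x 0.16 x (1.645 + 0.842)^2 / margin^2, which is 198 for 10 points and 88 for 15. Sixty per arm reaches 80% only for a margin near 18 points. If no margin can be justified, the estimates and intervals are enough by themselves.

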The supportive attentional control is a well-validated control condition, adapted from the website HealthWatch, originally created by Griffiths et al. (2012). The website is comprised of 12 modules related to general health and well-being. Each module contains health information as well as brief questionnaires probing into individual experience with and feelings regarding each topic. The modules provide information on topics such as oral health, cholesterol, and nutrition without alluding directly to anxiety, stress, or depression. For the current study, one of the original modules (“Bacteria & Foodborne Illnesses”) was replaced with a brief OCD-specific psychoeducation module. The rationale for replacing this module was two-fold: 1) Contamination is a commonly occurring OCD theme and providing detailed information on bacteria and foodborne illness would likely negatively impact symptoms for at least some participants, and 2) enhancing the control condition with brief OCD-specific psychoeducation and treatment rationale could help boost engagement and credibility. The brief questionnaires are a mix of forced-choice and open-ended questions. The information was sourced from public domain material published by US Government health sources. Each week participants in this condition will be asked to log in to the website, read the information, and fill out the questionnaires assigned for that week. New materials will be presented along approximately the same timeline as in which participants in the CBT arm unlock new modules in the CBT app. As in the CBT-app arm, passively collected sensor data through the Beiwe app will provide information on changes in participants’ location, movement, and phone usage (described below).

End-of-Treatment Feedback to Technologists: A subset of participants may meet with technologists from Koa Health (sponsor and Perspectives app developers), either in-person, via audio recorded telephone call, or via any Partners-approved, secure, HIPAA-compliant clinical video platform, such as Enterprise Zoom or Virtual Visit at the end of treatment. The purpose of this assessment is for the technology experts to obtain input and feedback on the usability and feasibility of the CBT app (see “Endpoint technologist interview,” attached). This meeting will take up to approximately 1 hour, and participants will be reimbursed \$25 for completing this interview.

Measures Descriptions

Diagnostic Measures

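### The H3.1 feasibility verdict rests only on drop-out relative to HealthWatch, so the app arm's own drop-out level does not limit the conclusion

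*Combined protocol and SAP*

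**What the plan says.** Section II, Exploratory Aim 2, hypothesises that "app-delivered CBT for OCD will be feasible (based on drop-out rates) and acceptable" to people with OCD. No drop-out level is named.

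Section VI.B, Hypothesis 3.1, makes this comparative: "Drop-out from app-delivered CBT for OCD will not be higher than drop-out from the supportive attentional control condition, which will indicate feasibility".

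Section VI.C, H3.1, gives the rule. Drop-out is a composite of missing Y-BOCS assessments and failure to use the app or website at least once in each interval between assessments. The arms are compared by logistic regression with a one-tailed test for higher odds in the app arm. A positive verdict follows thus: "if non-significant, we will interpret the results as an indication that the app-CBT treatment is feasible in comparison to the supportive attentional control condition". The converse is: "significantly higher odds of drop-out in the app-CBT condition would indicate a lack of feasibility".

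The same item lists refusal and drop-out rates and reasons by group among the things to be examined, and the opening of section VI tabulates drop-out by reason and arm. Neither place attaches an interpretation to the level. The only drop-out levels in the plan are in section VI.D. There, "we assumed a conservative drop-out rate of 20% by end of treatment" is a sample-size input, supported by cited rates of 17-20% for treatments with minimal to low therapist contact and about 40% for self-administered treatment without it.

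**The concern.** Whether people with OCD stay in app treatment is most naturally a question about the app arm itself. H3.1 answers a different question: whether app drop-out is significantly higher than drop-out from a general-health website. If both arms retained people equally badly, the prespecified reading would still be that the app is feasible. The reported drop-out table could show a high level beside that conclusion, and nothing in the plan would reconcile the two.

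Sections VI.B and VI.C also differ in what a favourable result means. The statistical methods limit it to feasibility in comparison with the control; the endpoint section does not. The unqualified version matches the Aim 2 claim and is therefore the one likely to be reported. What is at stake is the content of an exploratory claim, not the efficacy result.

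**Working it through.** **Inputs.** Target of 120 randomized (section III) at 1:1, so 120 / 2 = 60 per arm. Alpha is 0.05, the general level stated at the head of section VI.C, because H3.1 gives no other; the test is one-tailed, so the critical value is 1.645. The 20% drop-out level is the plan's assumption, and about 40% is a rate it cites (section VI.D). The 60% level is my assumption, used to show the behaviour of the rule.

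**The plan's own figure.** The documents give no operating characteristic for H3.1. The one design figure that uses drop-out is the sample size. A two-sample t-test with difference 0.76, SD 1.1, two-sided 0.05 and 90% power needs 46 per arm (power 0.906). Allowing for 20% drop-out, 46 / 0.80 = 57.5, so 58 per arm and 116 in total, as stated. The 20% is used there and nowhere in the feasibility rule.

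**The rule.** Let a and c be the numbers of drop-outs among 60 in the app and HealthWatch arms. The Wald statistic from the logistic regression is

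z = [ln(a/(60-a)) - ln(c/(60-c))] / sqrt[1/a + 1/(60-a) + 1/c + 1/(60-c)],

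and the app is called feasible if z < 1.645. For example:
- a = 12, c = 12 (20% in each arm): z = 0, feasible.
- a = 36, c = 36 (60% in each arm): z = 0, feasible.

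**Probability of a feasible verdict.** This is the sum, over all (a, c) with z < 1.645, of Bin(a; 60, pA) x Bin(c; 60, pC), enumerated exactly.

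| True app drop-out | True HealthWatch drop-out | P(called feasible) |
|---|---|---|
| 20% | 20% | 95.0% |
| 40% | 40% | 94.6% |
| 60% | 60% | 94.6% |
| 60% | 70% | 99.7% |
| 40% | 20% | 22% |
| 50% | 20% | 3% |
| 60% | 20% | 0.1% |
| 60% | 30% | 4% |

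In the equal-rate rows, likelihood-ratio and score tests give 94.4% to 95.0%. With 58 per arm the Wald results are 95.1% at 20% and 94.7% at 60%. The first three rows are simply 1 - alpha, as for any level-alpha comparison under equal rates; they show that the common level carries no weight. The last four show that a high app level does count when the control does clearly better.

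**What an app-arm estimate would show.** The 95% Wilson interval is [p + z²/2n ± z·sqrt(p(1-p)/n + z²/4n²)] / (1 + z²/n), with n = 60 and z = 1.96:
- 12 of 60 (20%): 11.8% to 31.8%.
- 24 of 60 (40%): 28.6% to 52.6%.
- 36 of 60 (60%): 47.4% to 71.4%.

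The intervals at 20% and 60% do not overlap, although the comparative rule gives the same verdict for both when the arms match.

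**The case against.** Several counter-arguments have force.

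- **App drop-out is half of the contrast.** A reader might infer that the rule can never tell a well-retained app from a poorly retained one. That is too strong: with HealthWatch at the plan's 20%, an app losing 60% would almost never pass. The defect appears when both arms lose people at similar rates, or when HealthWatch loses more.
- **Heavy HealthWatch abandonment is not established.** A reader might infer it from a site where "The modules provide information on topics such as oral health, cholesterol, and nutrition". But that arm also has a coach, an onboarding call, replies within 36 hours on weekdays, paid assessments and an OCD module added partly to help engagement. The documents do not predict high drop-out there, and the 60% level has no basis in them.
- **The level is already reported.** Rates by group are part of the H3.1 analysis, so readers will see them. This stands. The gap is that they have no role in the conclusion.
- **The positive conclusion in section VI.C is already relative.** True, but section VI.B and Aim 2 are not so limited, and the converse in section VI.C is unqualified too.
- **It is exploratory.** Also true, and no decision in the plan depends on it.

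Reading non-significance as support without a margin is a separate weakness. A well-designed non-inferiority test against HealthWatch would still leave the app arm's level out of the verdict.

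**Conclusion.** The point holds in limited form. Under equal true drop-out, the app is declared feasible about 95% of the time at 20%, 40% or 60%, and nothing in the plan lets the app arm's own level limit that conclusion. Poor app retention is picked up only when HealthWatch retains clearly better (22% declared feasible at 40% versus 20%; 0.1% at 60% versus 20%). Sections VI.B and VI.C also disagree on whether the favourable reading is relative or unqualified.

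These figures assume 60 per arm, one-sided 0.05, independent binomial drop-out and no covariates. Reading Aim 2 as a question about the app arm itself is an inference, though a natural one, since it refers only to drop-out rates.

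A reader might also take the cited 40% as the plan's mark of failure. The documents do not support that. It describes treatment without therapist contact, whereas the app arm has a coach, and nothing shows that the cited rates use H3.1's composite definition. The consequence is confined to an exploratory claim.

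**What to change.** In sections VI.B and VI.C:

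1. Make the app-arm drop-out proportion, under H3.1's own definition, with its 95% CI, the feasibility estimate.
2. Show it beside the assumed 20% and the 17-20% cited in section VI.D for treatments with minimal to low therapist contact, noting that those rates may define drop-out differently.
3. Keep the HealthWatch comparison, but word it in both directions only as drop-out relative to HealthWatch, not as showing feasibility or its absence. Use the same wording in both sections.
4. Set no pass/fail threshold from the 40% figure. If the sponsor wants a cut-off, it should be chosen in advance to suit the composite definition.

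The cost is a change of wording and one proportion with its interval; no new data are needed. The downside is that feasibility can no longer be claimed from a non-significant test alone.
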